REDCap	Research Electronic Data Capture
VO _{2max}	Peak Oxygen Uptake

PROTOCOL SUMMARY

Title:	Congenital Heart Disease Physical Activity Lifestyle Study (CHD-PALS)
Abstract:	Over 40,000 infants are born in the U.S. with congenital heart disease (CHD) each year, and with advancements in medicine, more than 90% of these individuals now live well into adulthood. This growing, and aging, population of CHD survivors is at risk for developing cardiac-related complications such as coronary disease, heart failure, and hypertension, which fortunately are responsive to lifestyle change. An American Heart Association (AHA) Scientific Statement highlights the important health benefits gained from increasing physical activity (PA) among children and adults with CHD, noting research evidence of better vascular health, reductions in hypertension, and lower rates of obesity. Despite this, evidence suggests that CHD survivors are less active than healthy controls, placing them at an elevated risk for preventable morbidity and premature mortality. Therefore, the currently study adapts a PA lifestyle intervention to adolescent emerging adult CHD survivors (ages 15-25) who have moderate to complex CHD with the goal of increasing MVPA and decreasing SB. The study is split into 2 phases; a total of 125 adolescent and caregiver dyads and emerging adults will participate in Phase 1 to determine participants' eligibility for Phase 2. Phase 2 is the randomized control trial in which a total of 70 adolescents and 30 emerging adults are randomized to either the comparison arm (Fitbit and exercise prescription) or the intervention arm (Fitbit, exercise prescription, AND videoconferencing sessions with a coach).
Population:	Participants: For Phase 1 we aim to recruit 85 adolescents (ages 15 – 18 at enrollment) and 40 emerging adults (ages 18 – 25 at enrollment), who have moderate to complex CHD, along with caregivers for adolescents. For Phase 2 we aim to recruit 70 adolescent and caregiver dyads (35 per arm) and 30 emerging adults (15 per arm).
Study Duration:	4 years (2017-2021)
Participation Duration:	Phase 1: 2 weeks Phase 2: 22 weeks with a 6-month follow-up assessment

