2 BACKGROUND INFORMATION AND SCIENTIFIC RATIONALE

2.1 Background Information

Congenital heart disease (CHD) comorbidities and cost

Over 40,000 infants are born in the U.S. with CHD each year, and with advancements in medicine, more than 90% of these individuals now live well into adulthood.¹⁻³ This growing, and aging, population of CHD survivors are at risk for developing cardiac-related complications such as coronary disease, heart failure and hypertension, which fortunately are responsive to lifestyle change.⁴ More than half of children and adolescents with surgically corrected CHD have signs of intimal hyperplasia, an atherosclerosis precursor, highlighting the importance of early intervention.⁵ Those with moderate and complex cardiac lesions⁴ are the ones in greatest need for intervention, as evidenced by significantly higher premature mortality rates as compared to the general population due to underlying cardiovascular issues.⁶ Increased rates of hospitalizations costing more than \$3.16 billion annually due to higher incidence of coronary artery disease and heart failure among CHD survivors can be mitigated by early lifestyle intervention.⁷

Physical activity (PA) engagement and benefits

An American Heart Association (AHA) Scientific Statement⁸ highlights the important health benefits gained from increasing PA among children and adults with CHD, noting research evidence of better vascular health, reductions in hypertension and lower rates of obesity. Positive health behaviors often decline during adolescence and emerging adulthood, and adolescents with CHD are no exception, which may lead to poor health behaviors in adulthood.⁹⁻¹² Furthermore, declines in PA are greater among girls, especially during adolescence.^{12,13} Similar sex differences have been reported among adolescents with CHD, such that males demonstrate higher cardiopulmonary exercise tolerance than females.¹⁴ Therefore, adolescence and emerging adulthood are an optimal developmental time during which to intervene by changing lifestyle habits, such as PA, to prevent greater morbidity in through adolescence into adulthood.

Sedentary behavior (SB) is a risk factor

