These studies also draw attention to the need for using objective measures of PA to inform interventions, including using time spent in MVPA, as assessed by an accelerometer, for inclusion criteria so that adolescents and emerging adults in need of intervention are targeted. In the current study, objective measures of MVPA will also be used to stratify random assignment of participants, as well as included as covariates in study analyses, thereby improving scientific rigor as compared to previous studies. This strategy will allow the detection of group differences with fewer participants and is in accordance with guidelines for clinical trials.³³ The current study will also examine change in peak oxygen uptake (VO_{2max}), a measure of exercise tolerance, as a secondary outcome. VO_{2max} has been identified as an independent predictor of 5-year mortality in young adult CHD survivors.³⁴ While change in VO_{2max} has been commonly assessed as an outcome in cardiac rehabilitation-style exercise interventions for CHD survivors, increased MVPA may not result in improved cardiorespiratory fitness. Current guidelines indicate that increasing moderate PA has significant health benefits, even in the absence of change in VO_{2max} .

Utilizing technology to facilitate behavior change: Videoconferencing and a popular activity tracker (Fitbit®)

Videoconferencing behavioral interventions have demonstrated feasibility in other adolescent chronic illness populations, including diabetes^{35,36} and inflammatory bowel disease,³⁶ as well as among adults at risk for cardiovascular disease.³⁷ Videoconferencing as a mode of delivery for

behavioral interventions has multiple advantages, such as eliminating some barriers to receiving the intervention (e.g., transportation, distance) and reducing costs for both providers and patients. Furthermore, videoconferencing and other modes of telehealth delivery have been shown to result in comparable rapport-building between youth and clinicians as face-to-face interventions and are accepted by families.³⁸ A Fitbit will be used in the current study as part of the intervention so that participants receive moment-to-moment feedback on their PA.

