5.3 Treatment Assignment Procedures

5.3.1 Randomization Procedures

The PI, study staff, and the research participant do not know the participant's arm designation until the envelope, which was prepared by the study statistician ([name]) is opened. Randomization is stratified by the number of minutes spent in MVPA per the accelerometer data in

Phase 1 (adolescents: <21 min/day of MVPA vs. \geq 21 min/day of MVPA; emerging adults: \leq 25 min/day of MVPA vs. \geq 26-59 min/day of MVPA) with randomly varying block sizes. Strata were based on the mean baseline levels of MVPA as reported in 2 studies of adolescents with CHD^{27,28} and 2 studies of emerging and middle-aged adults with CHD.^{30,32}

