7.9 Analysis Plan

Aim 1: Evaluate the feasibility of the intervention.

The mean/median ratings by participants on multiple dimensions of the intervention will be computed. Recruitment rate will be calculated as a percentage of those recruited out of those approached. Percent adherence across sessions will be calculated for those in the intervention arm as the number of sessions attended out of 8. The retention rate will be identified by dividing the number of participants who do not complete the study by the number of participants enrolled.

Verbal responses collected during the focus groups will be transcribed and then coded so that the frequencies of suggestions can be calculated.

Aim 2: Examine preliminary efficacy of the intervention on time spent in MVPA.

First, independent sample t-tests (continuous variables) or chi-square tests (categorical variables) will compare study arms on all variables at baseline, *including biological considerations such as sex and disease status*, to determine if statistically significant differences are present. Only the pre-specified covariates of baseline minutes spent in MVPA and baseline VO_{2max} will be included in the primary analyses.⁶² However, if statistically significant differences are found at baseline, those variables will be examined as covariates in all statistical models of interest in an exploratory fashion.

Second, the following statistical model for repeated measures (RM), based on maximum likelihood estimation, will be employed,⁶³ $y_{it} = \beta_0 + \beta_1 Time_t + \beta_2 Time_t \times Trt_i + \varepsilon_{it}$, where implicitly it is assumed that there is no main effect of Trt_i , y_{it} is minutes in MVPA at time t , $Time_t$ is coded as 0 for baseline and 1 for post-intervention, and the primary effect of interest is β_2 , which is the difference between groups on participants' minutes in MVPA. In this RM model, baseline levels of minutes in MVPA is constrained to have equal means across groups by assuming there is no main effect of the intervention, Trt_i . This constraint yields a statistical test for β_2 analogous to the test of the treatment group main effect per ANCOVA without requiring list-wise deletion to account for missing data. A similar strategy will be taken for analyzing change in SB and VO_{2max} as secondary outcomes.

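### Age cohort is in effect a randomisation stratifier but is left out of the primary model, so the reported standard error may be slightly too wide

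*Combined protocol and SAP*

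**What the plan says.** **Design.** Section 5.3.1 states: "Randomization is stratified by the number of minutes spent in MVPA per the accelerometer data in" Phase 1. The cut-points differ by cohort. Adolescents are split at 21 min/day; emerging adults are split into 25 or below and 26 to 59. The Protocol Summary (Population) plans "70 adolescent and caregiver dyads (35 per arm) and 30 emerging adults (15 per arm"). Together these give four randomisation cells, low and high MVPA within each cohort, with equal allocation intended in each cohort.

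**Analysis.** Section 7.9, Aim 2, restricts the primary analyses: "Only the pre-specified covariates of baseline minutes spent in MVPA and baseline" VO2max are to be included. The displayed repeated-measures model is y = β0 + β1·Time + β2·Time×Trt + ε, with one intercept and one time effect for everyone aged 15 to 25. Any other variable enters only in exploratory models, and only after a statistically significant baseline difference between arms. SB and VO2max are to be handled along similar lines, without further detail.

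**Stated reasoning.** Section 2.1 says that "objective measures of MVPA will also be used to stratify random assignment of participants, as well as included as covariates in study analyses", and gives as the reason that group differences can then be detected with fewer participants.

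**The concern.** When allocation is balanced within a factor, differences between the levels of that factor drop out of the true sampling error of the treatment effect. If the analysis omits the factor, those differences stay in the residual variance, and the reported standard error is larger than the design warrants.

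Continuous baseline MVPA does not stand in for the randomisation cell. A participant at 23 min/day is in the high stratum as an adolescent and in the low stratum as an emerging adult. The exploratory route will not correct the omission either, because stratification makes a significant cohort imbalance unlikely.

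What is at stake is the width of the confidence interval and a little power. Section 7.7 makes estimation of an initial effect size the primary goal, so an interval that reflects the design has some value.

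**Working it through.** **Plan's own figures.** The documents give no cohort effect on post-intervention MVPA, no SD in minutes and no baseline–post correlation, so there is no stated figure for this point to reproduce. The power figures in section 7.7 (80% for a large effect, 55% for d = 0.6, 50 per group) raise a separate question. At two-sided 5%, taking large as d = 0.8, 50 per group gives about 98% and 85%; the stated pair fits about 25 per group. They are not used below.

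**Inputs**
- Emerging-adult share p = 30/100 = 0.30, allocation 1:1 within cohort (Protocol Summary).
- δ: cohort difference in post-intervention MVPA that remains after the baseline covariates, in residual SDs. This is an assumption, shown over a range.

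**Formula.** Omitting a balanced two-level factor multiplies the residual variance by 1 + p(1 − p)δ². Since 0.30 × 0.70 = 0.21, the ratio of standard errors (cohort omitted / included) is √(1 + 0.21δ²).

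| δ | 0.21δ² | SE ratio | Inflation |
|---|---|---|---|
| 0 | 0 | 1.000 | 0% |
| 0.2 | 0.0084 | 1.004 | 0.4% |
| 0.33 | 0.0229 | 1.011 | 1.1% |
| 0.5 | 0.0525 | 1.026 | 2.6% |
| 0.8 | 0.1344 | 1.065 | 6.5% |
| 1.0 | 0.2100 | 1.100 | 10% |

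Inflation exceeds 5% only if δ > √((1.05² − 1)/0.21) = 0.70.

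**Which δ is plausible?** The only cohort contrast in the documents is the gap between cut-points, 21 against 25 or 26, so 4 to 5 min/day. Section 5.3.1 says the cut-points were based on mean MVPA in published studies. Suppose that gap holds at both visits. Then δ = gap × (1 − ρ) / (SD × √(1 − ρ²)), where ρ is the baseline–post correlation. With assumed SD 10 to 20 min and ρ 0.4 to 0.8:
- largest case (gap 5, SD 10, ρ 0.4): δ = 5 × 0.6 / (10 × 0.917) = 0.33, inflation 1.1%;
- smallest case (gap 4, SD 20, ρ 0.8): δ = 4 × 0.2 / (20 × 0.6) = 0.067, inflation 0.05%.

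To reach δ = 1.0 with ρ = 0.6 (residual SD 0.8), the cohorts would have to be equal at baseline and 0.8 SD apart at post-intervention. Nothing in the documents points to that.

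**Simulation check.** 6,000 trials per scenario under no treatment effect: 70 adolescents and 30 emerging adults, four strata, blocks of 2 or 4, ρ = 0.6. The analysis was ANCOVA, to which section 7.9 likens its own test, adjusted for baseline MVPA only.

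| δ | Mean model SE, omitted / included | Actual SD of estimate, omitted / included | Type I error, omitted / included |
|---|---|---|---|
| 0 | 0.1598 / 0.1599 | 0.1607 / 0.1607 | 5.2% / 5.2% |
| 0.2 | 0.1606 / 0.1599 | 0.1576 / 0.1576 | 4.7% / 4.8% |
| 0.5 | 0.1641 / 0.1600 | 0.1615 / 0.1615 | 4.2% / 4.8% |
| 0.8 | 0.1703 / 0.1599 | 0.1625 / 0.1617 | 4.0% / 5.2% |

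The Monte Carlo error of a 5% rate is √(0.05 × 0.95/6000), about 0.3 percentage points. The ratios of model SEs agree with the formula. The mean estimate was within 0.003 of zero throughout, and the actual spread barely moves. What changes is the reported standard error.

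**The case against.** The strongest reply is that the harm is conditional and probably small. It needs cohort to predict post-intervention MVPA beyond baseline MVPA and baseline VO2max, both already pre-specified, and the documents quantify no such effect. VO2max may absorb part of any cohort difference. Limiting a 100-person pilot to two covariates is a defensible choice, and section 2.1 speaks of adjusting for MVPA, not of a general rule for every stratifier. All of this stands, and it limits the size of the point. It does not favour leaving cohort out: at δ = 0 the term costs essentially nothing (0.1598 against 0.1599).

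It may also be said that section 5.3.1 never names cohort as a stratifier. That is true; it follows from the cohort-specific cut-points and the per-arm targets by cohort.

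Several stronger readings are tempting but not supported:
- That the standard error is too wide as a matter of fact. Without a residual cohort effect there is no inflation.
- That the benefit of stratifying is lost or β2 is biased. Balance is kept and the estimator's true variability is almost unchanged.
- That a fifth of the sample is wasted. Even at δ = 1.0, the variance ratio of 1.21 means 21% more participants for equal precision, or 1 − 1/1.21, about 17%, of the sample; and that δ is an extreme case.
- That the SB and VO2max models omit baseline MVPA. Section 7.9 is ambiguous and could be read as keeping both covariates.
- That sex must be added on the same grounds, given the remark in section 2.1 that "declines in PA are greater among girls, especially during adolescence". Sex is not a stratifier. Section 4 lists it as a possible covariate or moderator, and section 7.9 compares the arms on it at baseline and explores it as a moderator.

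**Conclusion.** The omission is clear from the text, and its direction is certain: the reported standard error of β2 can be too wide because of it, not too narrow, so the test errs on the conservative side. The size is uncertain because δ is not given. An inflation of 0–3% is most plausible, corresponding to δ up to about 0.5; 6.5% at δ = 0.8 and 10% at δ = 1.0 are upper scenarios. This rests on the planned 70/30 split with equal allocation within cohort. It is a modest improvement worth making because it is nearly free, and it does not threaten the validity of the primary result.

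**What to change.** In section 7.9:
- **MVPA model:** add cohort (adolescent or emerging adult, as recorded at randomisation) and cohort × time to the pre-specified terms, and amend the sentence that admits only two covariates. Use the recorded cohort, not age, since the two age ranges in the Protocol Summary meet at 18.
- **SB and VO2max models:** name the terms explicitly. Include either the four-level randomisation stratum with its time interaction, or cohort plus baseline MVPA with their time interactions.

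Cost: two extra parameters for MVPA (one main effect, one interaction) and up to six for each secondary outcome (three stratum contrasts plus three interactions). The change is to wording only, with no new data and no change to conduct.

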5.3.3 Handling of Withdrawals

If withdraw occurs because a participant's cardiologist determines that the participant should no longer be in the study due to a change in medical status or the participant and/or caregiver request to be withdrawn, participants are asked to complete the assessments if possible and are included in intent-to-treat analyses.

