MVPA and SB: Participants receive a triaxial accelerometer (ActiGraph, model wGT3X-BT), sensitive to movement in all directional planes, to measure the amount of time spent in sedentary, light, moderate, and vigorous PA. The accelerometer is worn around the waist for 7 days for at least 10 hours per day, only to be removed when showering or submerging in water (e.g., swimming). Participants will also complete self-monitoring PA logs in the case they cannot wear the accelerometer (e.g. swimming). If baseline accelerometer and self-monitor PA log data indicate that a participant averages at least 60 minutes of MVPA per day, they are not eligible for Phase 2.

Compensation: Caregivers are compensated \$20 after they complete the baseline surveys. Participants are compensated \$100 for completing the baseline survey, exercise stress test, and wearing the accelerometer for at least 4 days (1 weekend day, 3 weekdays), for at least 10 hours per day. Additionally, participants' parking and mileage to/from the hospital for the exercise stress test are reimbursed.

Contact and Scheduling. If the participant is eligible for the Phase 2, they are contacted by phone and asked to schedule a home visit, within 8 weeks from their exercise stress test, if interested in participating.

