6.4 Interim Assessment (between weeks 8-12)

Participants in both arms are asked to complete an interim assessment (between weeks 8-12), which includes:

Interim online questionnaire: Participants are asked to complete the same questionnaire that was completed at Baseline, with the exception of those in the comparison arm receiving questions about changes to their health since Baseline.

- Benefits of PA⁵⁰

- Subjective Norms survey⁵¹

- Social Support for Exercise survey⁵²

- Barriers to Exercise survey⁵³

- Self-Efficacy for Exercise Scale⁵⁴

- Patient-Reported Outcomes Measurement Information System⁴⁵⁻⁴⁷

- International Physical Activity Questionnaire^{48,49}

- Cardiac Anxiety Questionnaire⁵⁵

- Changes in Health

MVPA and SB: Participants wear an accelerometer again for the same period (7 days) as the Baseline assessment and complete self-monitoring PA logs in the case they cannot wear the accelerometer (e.g. swimming).

Compensation: Participants are compensated \$50 for completion of the interim assessment survey and wearing the accelerometer for at least 4 days (1 weekend day, 3 weekdays), for at least 10 hours per day.

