6.6 Focus Groups (after post-intervention assessment)

Participants in the intervention arm are asked to partake in a focus group lasting approximately 1.5 hours, to discuss their experiences in the study. There will be 3-4 groups that meet via videoconferencing with 6-8 participants per group.

Compensation: Participants are compensated \$50 for being in the focus group.

6.7 6-Month Follow-up (between weeks 46-50)

Participants in both arms are asked to complete a 6-month follow-up assessment (between weeks 46-50), which includes:

6-month follow-up online questionnaire: Participants are asked to complete the same questionnaire that was completed at the interim assessment.

- Benefits of PA⁵⁰

- Subjective Norms survey⁵¹

- Social Support for Exercise survey⁵²

- Barriers to Exercise survey⁵³

- Self-Efficacy for Exercise Scale⁵⁴

- Patient-Reported Outcomes Measurement Information System⁴⁵⁻⁴⁷

- International Physical Activity Questionnaire^{48,49}

- Cardiac Anxiety Questionnaire⁵⁵

- Changes in Health

MVPA and SB: Participants wear an accelerometer again for the same measurement period (7 days) as in previous assessments and complete self-monitoring PA logs in the case they cannot wear the accelerometer (e.g. swimming).

Compensation: Participants are compensated \$75 for completion of the 6-month follow-up assessment survey and wearing the accelerometer for at least 4 days (1 weekend day, 3 weekdays), for at least 10 hours per day.

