7.7 Sample Size Considerations

A sample size of $n=50$ per group will provide 80% power to detect a large effect size⁵⁹ for the standardized mean difference, still allowing for possible detection of a medium effect size ($d=.6$) with 55% power. Effect sizes from relevant studies examining change in MVPA range from large ($d=.94$; CHD adolescents in a motivational interviewing-style exercise intervention)²⁸ to small ($d=.17$; older adults with cardiovascular risk factors).²² Thus, our primary goal is to estimate an initial effect size for our intervention in our population, with a secondary goal to detect large effect sizes that may exist for study outcomes. However, effect estimation with a relatively small sample size should be interpreted with caution, as it may under or overestimate the sample size.^{60,61}

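### The primary MVPA model uses two of the four accelerometer waves, so a participant without a post-intervention value adds essentially nothing to the treatment effect

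*Combined protocol and SAP*

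**What the plan says.** Section 7.9 (Aim 2) sets y = β0 + β1·Time + β2·Time×Trt + ε, where Time "is coded as 0 for baseline and 1 for post-intervention" and β2 is the primary effect. There is no treatment main effect, so the arms share a baseline mean. No within-person covariance is named. The stated attraction is a test like that of ANCOVA "without requiring list-wise deletion to account for missing data".

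Baseline MVPA is known for everyone randomised. Section 5.3.1 says "Randomization is stratified by the number of minutes spent in MVPA per the accelerometer data", and under section 6.2 a participant who "averages at least 60 minutes of MVPA per day, they are not eligible for Phase 2".

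Two further accelerometer waves are collected in both arms. Section 6.4 (weeks 8-12) says "Participants wear an accelerometer again for the same period (7 days) as the Baseline assessment", and section 6.7 says "Participants in both arms are asked to complete a 6-month follow-up assessment (between weeks 46-50", again with 7 days of wear. Section 7.9 uses the interim visit by name only for the Theory of Planned Behavior mechanisms in Aim 3. It names no analysis of 6-month MVPA.

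On withdrawals, section 5.3.3 says "participants are asked to complete the assessments if possible and are included in intent-to-treat analyses". Section 7.7 says "our primary goal is to estimate an initial effect size for our intervention in our population".

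**The concern.** The missing-data advantage claimed for the model is formally true, since no record is deleted. With only two times and a complete baseline, however, it brings no practical gain for MVPA: people without a post value are in the data set but do not inform β2. The intent-to-treat promise in section 5.3.3 is then nominal for them.

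The two-wave estimate is valid if loss depends only on arm and the baseline covariates. It can be biased if loss after the interim visit depends on interim activity and interim activity predicts the post value. The design makes this credible, though it does not prove it. The post-intervention visit adds a hospital stress test that the interim visit does not require. Coached participants are asked to sync their Fitbit daily, while the comparison arm is not contacted about the Fitbit again (section 5.7). Because the effect estimate is itself the main product of this pilot, bias in it carries straight into planning of the next trial.

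**Working it through.** The plan gives no bias, correlation or dropout figure to reproduce. The inputs from the documents are 50 per arm, retention of at least 75% (so up to 25 of 100 lost) and the two-wave model. Everything else below is assumed.

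**Step 1: what the two-wave likelihood uses.** With an unstructured covariance common to both arms and only the post value y1 missing, the likelihood factors into f(y0; β0, σ00) over all randomised and f(y1 | y0; a + β2·Trt + b·y0, σ1·0) over completers, where a = β0 + β1 − b·β0. The two parameter sets are distinct, so

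β2-hat = (ȳ1T − ȳ1C) − b-hat·(ȳ0T − ȳ0C),

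with every mean taken over completers. This is completers-only ANCOVA. With independent errors b = 0, and β2-hat is the raw difference in observed post means. At 25% loss β2 rests on 100 − 25 = 75 people.

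**Step 2: numerical check.** In 200 simulated data sets the two-wave ML estimate and completers-only ANCOVA differed by at most 1.3e-11 min. Five further data sets (n = 100, 21-33 post values missing) show the effect of the unnamed covariance, in minutes:

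| Data set | Unstructured | Completers ANCOVA | Compound symmetry | Independent errors |
|---|---|---|---|---|
| 1 | 8.2632 | 8.2632 | 8.3804 | 10.2083 |
| 2 | 4.4268 | 4.4268 | 4.4261 | 4.4528 |
| 3 | 8.0727 | 8.0727 | 8.2120 | 9.8241 |
| 4 | 5.0936 | 5.0936 | 5.1920 | 5.9922 |
| 5 | 2.6539 | 2.6539 | 2.8166 | 3.7101 |

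The covariance choice moves the estimate by up to 10.2083 − 8.2632 = 1.95 min.

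**Step 3: bias when loss depends on interim MVPA.** There were 3,000 simulated trials per scenario, with 50 per arm and true effects of 0.4, 0.6 and 0.4 SD at interim, post and 6 months. Correlations (baseline-interim / baseline-post / interim-post) were A 0.5/0.5/0.5, B 0.6/0.5/0.7 and C 0.7/0.7/0.7. Lower interim MVPA raises the log-odds of a missing post value by the slope shown, per SD. In the coached-arm rows, comparison-arm loss is random. In the both-arms rows, one rule applies to everyone, so the comparison arm, with its lower interim mean, loses more. Everyone lost has an interim value.

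| Loss driven in | Missing | Slope | Two-wave A | B | C |
|---|---|---|---|---|---|
| Coached arm | 25% | 0.5 | 0.626 | 0.645 | 0.622 |
| Coached arm | 25% | 1.5 | 0.673 | 0.714 | 0.662 |
| Both arms | 25% | 0.5 | 0.595 | 0.595 | 0.596 |
| Both arms | 25% | 1.5 | 0.579 | 0.566 | 0.584 |
| Coached arm | 15% | 1.5 | 0.646 | 0.670 | 0.640 |
| Both arms | 15% | 1.5 | 0.584 | 0.575 | 0.585 |

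The four-wave model gave 0.596 to 0.603 in every row. The extreme two-wave shifts are 0.714 − 0.600 = +0.114 and 0.566 − 0.600 = −0.034. The estimate's SD is 0.16-0.20, so the larger shift is about 0.6 of an SD. Simulation error is at most 0.20/√3000 = 0.004.

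A separate check in minutes (SD 15, true effect 9, 25% loss, 300 data sets per scenario) added only the interim wave and included loss running in opposite directions in the two arms. Two-wave bias of −0.9 to +3.0 min fell to −0.2 to +0.4 min, with simulation error of about 0.2 min.

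**Step 4: where the extra waves help less** (coached arm, slope 1.5, 25% missing).

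| Pattern | Two-wave A, B, C | Four-wave A, B, C |
|---|---|---|
| Half of those lost also miss the interim visit | 0.669, 0.710, 0.667 | 0.627, 0.639, 0.629 |
| Loss depends on the unseen post value | 0.812, 0.816, 0.750 | 0.789, 0.741, 0.724 |

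Under completely random loss both models are unbiased. The four-wave variance is lower by 3.3%, 10.1% and 4.1% at 25% missing, and by 1.3%, 4.7% and 2.4% at 15%.

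**Step 5: the planned VO2max covariate.** If baseline VO2max enters with one coefficient shared by both times (correlation 0.3 with MVPA, SD 15 min, 25% random loss, 150 data sets), two-wave ML differs from complete-case ANCOVA by 0.22 min on average and 1.5 min at most. In 120 trials with coached-arm loss driven by interim MVPA (set B), the two-wave mean was 0.756, completers ANCOVA 0.754 and the three-wave model 0.648, with simulation error of about 0.02. The gap of 0.756 − 0.648 = 0.108 is close to the 0.114 above, so the covariate does not rescue the two-wave model.

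**The case against.** Hypothesis 2 is set at post-intervention and the model targets exactly that contrast, so this is a weakness in the analysis, not a contradiction. That stands, and so does the same reading of the 6-month wave: its absence from section 7.9 is a reporting gap.

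The bias sizes are assumed. The upper figure of 0.71 needs 25% loss, a strong link and loss driven by interim activity in the coached arm. A weak link gives 0.62-0.65, and one common rule in both arms gives a small shift the other way. The 25% is a predicted retention floor, not a forecast of missing post-intervention accelerometer data, and asking withdrawn participants for assessments should reduce it. All of this stands and limits the claim about size, but not the algebra.

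The remedy is weakest where loss does most harm, as Step 4 shows. With the VO2max covariate the equality with ANCOVA is close, not exact, hence *essentially* nothing. Interim MVPA might also enter the Aim 3 mediation models, though section 7.9 does not say so; the point here is confined to Aim 2. None of these objections points to a passage that brings the other waves into the primary analysis.

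**Conclusion.** The point holds. As written, β2 for MVPA is in effect a completers-only estimate, and the ML fit gives no practical protection against a missing post value. That part is algebra and needs only a complete baseline and a covariance common to both arms.

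The consequence for bias is conditional. Under the Step 3 assumptions the two-wave mean lies between 0.57 and 0.71 for a true 0.60; its sign depends on who is lost. Including the collected waves removes this bias if loss is explained by observed activity and those lost have an interim value, and reduces it otherwise. The change should be made because an effect estimate is the stated primary goal and the data are already collected.

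**What to change.** For MVPA and SB, keep the baseline-constrained ML model but fit four categorical times (baseline, interim, post-intervention, 6 months), with arm by each post-baseline time and an unstructured covariance named in the plan. Keep arm by post-intervention as the single primary contrast, and report arm by 6 months as secondary or exploratory. State the missing-at-random assumption. If the model does not converge, drop the 6-month wave: three- and four-wave post-intervention means differed by at most 0.008.

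The cost is SAP wording; there are no new data, visits or participants. Covariance parameters rise from 3 (2×3/2) to 10 (4×5/2), or to 6 (3×4/2) in the fallback. The VO2max analysis has the same two-wave limit, but only two stress tests are done, so this change cannot help it.
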